In this phase, safety and tolerability will be further evaluated in an expanded cohort of 9 subjects at the RP2D of CyPep-1, determined in Phase I. Screening- and treatment-schedules will be the same as in Phase I, except for the 24-h observation period before start of treatment of the next subject, which is not applicable.

At the RP2D, in case of a responder per iRECIST or of 2 subjects with stable disease per iRECIST, the number of subjects will be expanded to a total of 18 (to evaluate overall data from a total of 24 subjects treated at RP2D for CyPep-1 monotherapy taking the 6 subjects from cohort 3 into account).

Replacement of subjects in the Phase IIa expansion monotherapy arms is not planned.

Phase IIa – combination arm (Arm B):

The safety and tolerability of CyPep-1 in combination with pembrolizumab will be evaluated in a cohort of 15 subjects in total, using a staggered approach. Initially, 3 subjects will receive CyPep-1 at RP2D in combination with pembrolizumab Q6W and each subject will be observed for 24 h before the next subject can be administered with CyPep-1. After the first 3 subjects completed the TLT observation period of 6 weeks with no TLTs observed and after reviewing the safety data (including TLTs) by the DEC, the inclusion of all remaining subjects at RP2D of CyPep-1 in combination with pembrolizumab can be initiated. In the absence of any TLTs in the initial 3 subjects, the 24-h observation period before start of treatment of the next subject is no longer applicable. Should any TLTs be observed in the first 3 subjects at the RP2D of CyPep-1 in combination with pembrolizumab, an additional 3 subjects in this dose group will be included. If ≤1 out of 6 subjects have a TLT, the remainder of the 15 subjects will be treated at the RP2D. In the unlikely case that 2 or more of the 6 subjects experience any TLTs at RP2D of CyPep-1, a recommendation to dose de-escalate CyPep-1 and to what dose or to continue the combination part of the trial will be made by the DEC. The same screening schedule is planned and CyPep-1 will be administered according to the same treatment schedule as in Phase I.

For arm B, replacement of the first three subjects is allowed if a subject drops out for any reason, and does not receive all three CyPep-1 injections during the TLT observation period, unless due to CyPep-1- and/or pembrolizumab-related toxicity. No subject replacement will occur for subjects who discontinue later.

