For Arm B, on the visits that CyPep-1 and pembrolizumab are administered on the same day, CyPep-1 is planned to be administered 30 to 60 min after pembrolizumab has been administered. In case of pembrolizumab-related toxicity, treatment with CyPep-1 will be delayed and planned after a review by the investigator and medical monitor. If CyPep-1 treatment is delayed > 7 days, that dose will be omitted. If the delay of > 7 days is during the TLT observation period, the subject will be replaced.

For Phase I, Phase IIa Arms A and C, CyPep-1 administration is planned as Q2W injections. If CyPep-1 treatment is delayed > 7 days, that dose will be omitted. If CyPep-1 treatment is delayed for > 6 weeks during the DLT period (first 3 injections), the subject should be discontinued from the trial.

For Arm D, CyPep-1 administration is planned as QW injections until the second iRECIST/itRECIST assessment at week 16, followed by a Q2W dosing scheme. In case CyPep-1 treatment is delayed for > 3 weeks (first 3 injections), the investigator and the Medical Monitor must assess on a case-by-case basis the decision whether the subject should be discontinued from the trial. Treatment delay due to TEAEs will be considered for treatment discontinuation.

Radiological assessment to determine occurrence of (un)confirmed PD will be performed Q8W from the start of treatment for all trial phases and arms. Treatment will continue until confirmed PD, unacceptable toxicity, death or consent withdrawal, loss to follow up, or trial end, whichever occurs first.

DOSE LIMITING TOXICITY:

A DLT is defined by the occurrence of any of the following toxicities according to CTCAE v5.0 during treatment Cycle 1 and that are considered by the investigator to be possibly, probably, or definitely related to CyPep-1:

1. Any Grade ≥ 3 AEs of any etiology, except:
 - Nausea, vomiting, or diarrhea will be considered a DLT only if it persists at Grade ≥ 3 for > 3 days despite adequate supportive care measures. At the investigator's

discretion, subjects who experience nausea, vomiting, or diarrhea after receiving CyPep-1 may receive antiemetic or anti-diarrheal medication prior to subsequent doses of CyPep-1.

- Isolated laboratory abnormalities Grade ≥ 3 (not present at baseline) that resolve to Grade ≤ 1 in ≤ 7 days without clinical sequelae or need for therapeutic intervention.
- Fatigue Grade ≥ 3 for ≤ 7 days.

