In case in the first 12 subjects at RP2D, a responder per iRECIST (ORR as CR/PR as best response) or 2 subjects with stable disease (SD with duration >16 weeks from onset) per iRECIST are observed, the number of subjects will be expanded to a total of 24 (CyPep-1 monotherapy; subjects cohort 3 of Phase I and in Phase IIa Arm A).

Phase IIa – combination arm (Arm B):

The safety and tolerability of CyPep-1 in combination with pembrolizumab will be evaluated in a cohort of 15 subjects in total, using a staggered approach. Initially, 3 subjects will receive CyPep-1 at RP2D in combination with pembrolizumab and each subject will be observed for 24 h before the next subject can be administered with CyPep-1. After the first 3 subjects completed the TLT observation period of 6 weeks with no TLTs observed and after reviewing the safety data (including TLTs) by the DEC, the inclusion of all remaining subjects at RP2D of CyPep-1 in combination with pembrolizumab can be initiated. In the absence of any TLTs, the 24-h observation period before start treatment of the next subject is no longer applicable. Should any TLTs be observed in the first 3 subjects at the RP2D of CyPep-1 in combination with pembrolizumab, an additional 3 subjects will be included in this dose group. If ≤1 out of 6 subjects have a TLT, the remainder of the 15 subjects will be treated at the RP2D. In the unlikely case that 2 or more of the 6 subjects experience any TLTs at RP2D of CyPep-1, a recommendation to dose de-escalate and to what dose or to continue the combination part of the trial will be made by the DEC. The same screening is planned, and CyPep-1 will be administered according to the same schedule as in Phase I.

Scheduling of treatment of CyPep-1 and pembrolizumab (Arm B) will be as follows: CyPep-1 will be administered every 2 weeks (Q2W) and pembrolizumab will be administered following a Q6W schedule starting on Day 1, as per standard of care. Radiological assessment to determine occurrence of (un)confirmed PD will be performed Q8W from the start of treatment. Treatment will continue until confirmed PD, unacceptable toxicity or consent withdrawal, loss to follow up, or trial end, whichever occurs first.

Phase IIa – dose expansion liver metastases (Arm C):

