3. Any non-hematologic AE \geq Grade 3 in severity should be considered a TLT, with the following exceptions: Grade 3 fatigue lasting ≤ 3 days; Grade 3 diarrhea, nausea, or vomiting without use of anti-emetics or anti-diarrheal per standard of care; Grade 3 rash without use of corticosteroids or anti-inflammatory agents per standard of care.
4. Any Grade 3 or Grade 4 non-hematologic laboratory value if:
 - Clinically significant medical intervention is required to treat the participant or
 - The abnormality leads to hospitalization, or
 - The abnormality persists for > 1 week.

- The abnormality results in a Drug-induced Liver Injury (DILI)
- Exceptions: Clinically nonsignificant, treatable, or reversible laboratory abnormalities including liver function tests, uric acid, etc.

5. Febrile neutropenia Grade 3 or Grade 4:

- Grade 3 is defined as ANC <1000/mm³ with a single temperature of >38.3 degrees C (101 degrees F) or a sustained temperature of ≥38 degrees C (100.4 degrees F) for more than 1 hour
- Grade 4 is defined as ANC <1000/mm³ with a single temperature of >38.3 degrees C (101 degrees F) or a sustained temperature of ≥38 degrees C (100.4 degrees F) for more than 1 hour, with life-threatening consequences and urgent intervention indicated.

6. Prolonged delay (>2 weeks) in initiating Cycle 2 due to treatment-related toxicity.

7. Any treatment-related toxicity that causes the participant to discontinue treatment during Cycle 1.

8. Missing >25% of CyPep-1 doses as a result of drug-related AE(s) during the first cycle.

9. Grade 5 toxicity.

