4.3.2 Replacement of Subjects

In Phase I, replacement for subjects who drop out for any reason, except DLTs, will only occur before the DLT observation period is completed and is allowed if a subject does not receive all three CyPep-1 administrations, unless due to CyPep-1-related toxicity.

No subject replacement will occur for subjects who withdraw later or for subjects who are part of the Phase IIa expansion monotherapy Arms A and D.

For Arm B, replacement of the first 3 subjects is allowed if a subject drops out for any reason, and does not receive all three CyPep-1 injections of the first cycle, unless due to CyPep-1 and/or pembrolizumab related toxicity (TLT) during the TLT observation period. In case of pembrolizumab-related toxicity, treatment with CyPep-1 will be delayed and planned after a review by the investigator and medical monitor. If CyPep-1 treatment is delayed > 7 days, that dose will be omitted. If the delay is > 7 days during the TLT observation period, the subject will be replaced. No subject replacement will occur for subjects who discontinue later.

For Arm C, replacement for subjects who drop out for any reason, except DLTs, before the DLT observation period is completed is allowed when a subject did not receive all three CyPep-1 administrations. No subject replacement will occur for subjects who discontinue later.

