For Phase IIa Arms A and B, for a lesion > 7 cm, the same lesion should be considered to be injected weekly with up to 4 mL of CyPep-1 for the first 6 weeks (on Day 1, 8, 15, 22, 29 and 36), independent of the potential change in lesion size, followed by Q2W 4 mL administrations of CyPep-1. The visits on Days 1, 15, 29 and 36 will follow the assessments as per schedule. The visits on Days 8 and 22 will follow the assessments as per D15 (C1V2; excluding central lab sampling for cytokine analysis and blood sampling for immune cell phenotyping).

For Phase IIa Arm D, the to-be-injected volume for injection is preferably divided over as many lesions as possible. The longest diameter of the lesions for injection is ideally smaller than 2 cm and should not exceed 5 cm.

For subjects in Arms A, B and C, the injection volume will be:

Measured Lesion Diameter (cm)	Injected volume (mL)
≤ 1	1
> 1 and ≤ 2	2
> 2	4

For subjects in Arm D, the injection volume will be:

Measured Lesion Diameter (cm)	Injected volume (mL)
≤ 0.79	0.1
0.80 to 0.99	0.2
1.00 to 1.24	0.5
1.25 to 1.50	1.5
1.51 to 2.49	3.0
≥ 2.50	4.0

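### Arm B's >7-day replacement rule conflicts with its toxicity exception and can remove a TLT subject from the gate; the 'any TLTs' step also enrols three more subjects after the gate has already failed

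*Protocol*

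**What the plan says.** **Replacement in Arm B.** Protocol 4.3.2 allows any of the first three subjects to be replaced after dropping out without all three Cycle 1 injections, "unless due to CyPep-1 and/or pembrolizumab related toxicity (TLT) during the TLT observation period". The synopsis and SAP 6.1 carry the same exception: "CyPep-1 injections during the TLT observation period, unless due to CyPep-1- and/or pembrolizumab-related toxicity".

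The same paragraph of 4.3.2 continues: "In case of pembrolizumab-related toxicity, treatment with CyPep-1 will be delayed and planned after a review by the investigator and medical monitor". A dose delayed by more than 7 days is omitted, and then: "If the delay is > 7 days during the TLT observation period, the subject will be replaced". The synopsis (dose escalation and schedule, Arm B) follows the same sequence and ends: "If the delay of > 7 days is during the TLT observation period, the subject will be replaced". Section 4.3.1 repeats the omission and replacement steps in its bullet on intervention-related toxicity. None of the three places attaches a toxicity exception to this sentence. SAP 6.1 does not contain it.

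**What counts as a TLT.** Criterion 8 in Protocol 3.1.2 is: "Missing >25% of CyPep-1 doses as a result of drug-related AE(s) during the first cycle". Cycle 1 has CyPep-1 on Days 1, 15 and 29. For a lesion over 7 cm, Protocol 5.3.1.2 asks that it be considered for being "injected weekly with up to 4 mL of CyPep-1 for the first 6 weeks", which is six doses.

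**The gate.** Protocol 3.1: "Should any TLTs be observed in the first 3 subjects at the RP2D of CyPep-1 in combination with pembrolizumab, an additional 3 subjects" join the same dose group. With at most 1 TLT in 6, the remainder of the 15 are treated at the RP2D. With 2 or more of the 6, the DEC recommends whether to de-escalate or continue. No branch covers 2 or 3 TLTs among the first three.

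**The concern.** The two replacement rules give opposite instructions for the same patient, and no precedence is stated. The exception belongs to a permissive sentence about drop-outs and names only the first three subjects. The >7-day sentence is mandatory. If the gate expands to six, it is the only replacement text that could reach subjects 4 to 6.

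TLTs are a primary endpoint for the combination, and this gate is Arm B's only numeric TLT rule. It decides whether the remaining 12 subjects (15 − 3) or 9 subjects (15 − 6) go straight on to the combination. Two sites, or two DEC members, could handle the same delayed subject differently. If a replaced subject's TLT falls out of the count, a toxic combination passes more often.

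The second issue is exposure. After 2 or 3 TLTs in three subjects the pass condition cannot be met, yet the text still enrols three more at that dose. The Phase I table in Protocol 3.1 ties its three additional subjects to 1 DLT in 3; the Arm B wording has no such limit.

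**Working it through.** The plan states no operating characteristics for this gate (the 15 subjects rest on clinical considerations), so there is no figure to reproduce.

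**1. Does one omitted dose meet criterion 8?** The threshold is more than 25% of Cycle 1 CyPep-1 doses.

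- Q2W, three doses: 1/3 = 33.3%, so one omission due to a drug-related AE is a TLT.
- Weekly, six doses: 1/6 = 16.7%, not a TLT by this criterion; 2/6 = 33.3% is.

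On the standard schedule, the case the >7-day sentence describes (pembrolizumab toxicity, delay, omission) is therefore a TLT.

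**2. Effect on the gate if replaced TLTs are not counted.** Let p be the true TLT rate per subject. With all TLTs counted, the gate passes on 0 of 3, or on 1 of 3 followed by 0 of 3:

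P(pass) = (1−p)³ + 3p(1−p)² × (1−p)³

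At p = 0.30: 0.343 + 0.441 × 0.343 = 0.494.

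Let f be the share of TLT subjects whose only TLT is the dose omission and who are replaced and dropped from the count. The documents give no value; 10% to 50% is assumed. The TLT rate among counted subjects becomes

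p_eff = p(1−f) / (1−pf)

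At p = 0.30, f = 0.25: 0.225/0.925 = 0.243, and P(pass) = 0.433 + 0.418 × 0.433 = 0.614.

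| True TLT rate | All TLTs counted | f = 10% | f = 25% | f = 50% |
|---|---|---|---|---|
| 20% | 71% | 74% | 80% | 89% |
| 25% | 60% | 64% | 71% | 83% |
| 30% | 49% | 54% | 61% | 76% |
| 35% | 40% | 44% | 52% | 68% |

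A milder reading lets the exception protect the first three, so that only subjects 4 to 6 are replaced:

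P(pass) = (1−p)³ + 3p(1−p)² × (1−p_eff)³

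At p = 0.30 this gives 51%, 53% and 59% for f = 10%, 25% and 50%, against 49%. If replaced TLTs are counted, every cell equals the second column.

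**3. The 'any TLTs' step.** The chance that two or more of the first three have a TLT, with three more still enrolled, is 3p²(1−p) + p³:

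| True TLT rate | P(2 or 3 of 3) |
|---|---|
| 20% | 10.4% |
| 25% | 15.6% |
| 30% | 21.6% |
| 35% | 28.2% |

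At 30%, those three extra subjects carry 3 × 0.30 = 0.9 expected TLTs. P(pass) is unaffected, because 2 of 3 can never become 1 of 6.

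**The case against.** **The exception may govern.** A toxicity-related omission on the three-dose schedule is itself a TLT, so it falls under the bar, and the >7-day sentence could be read as subject to that bar. The later document, the SAP, carries only the exception. But this reading leaves the >7-day sentence nothing to do, on the standard schedule, in the very case its own paragraph introduces. The copies in the synopsis and 4.3.1 also stand apart from the exception.

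**Subjects 4 to 6 may not be meant.** The paragraph in 4.3.2 opens with the first three. That is fair for 4.3.2; the other two copies have no such limit.

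**Replaced TLTs may well be counted.** Section 4.3.1 keeps withdrawn subjects' data in the analyses, the Safety Analysis Set is everyone dosed, and SAP 11.1.3 tabulates TLTs for Arm B. This stands for the final report: those tables are unaffected by replacement. It does not settle who counts in the 1-of-6 decision. SAP 7.3 leaves DEC analyses to the Cohort Management Plan, which is not among the documents.

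**f is assumed, and toxicity causing a long delay may meet another TLT criterion.** Both are true. But the >7-day sentence would replace such a subject too, so omission-only TLTs are not the full reach of the rule.

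**The DEC can act sooner.** Protocol 3.1.1 lets it de-escalate on available data, 3.4 provides for enrolment holds, and 2 or more of 6 triggers a recommendation rather than a stop. These powers are discretionary and do not change the written instruction to enrol three more.

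**The gate may already be past.** The documents do not state its status.

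**Conclusion.** The concern holds on both parts.

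The replacement conflict follows from the text and the 33% arithmetic, with no assumption needed. Its effect on the gate is conditional. If replaced TLTs are not counted and f lies between 10% and 50%, the pass probability at a true TLT rate of 30% rises from 49% to between 54% and 76%, or to between 51% and 59% if only subjects 4 to 6 are affected. If they are counted, it does not change. The documents leave that open.

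The expansion step does not raise the chance of a wrong pass. It exposes three more subjects to a dose that can no longer meet the pass condition, with probability 10% to 28% at true TLT rates of 20% to 35%.

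**What to change.** 1. In the synopsis, 4.3.1 and 4.3.2, state that a subject meeting any TLT criterion, including criterion 8, is counted at the gate and is never replaced, and that this applies to the first three and, if enrolled, subjects 4 to 6. Limit replacement for a delay over 7 days to omissions not caused by drug-related AEs.
2. In the synopsis and 3.1, make the Arm B step: exactly 1 TLT in the first three adds three subjects; 2 or more go straight to the DEC, with no further enrolment at that dose until it has decided. At a true TLT rate of 30%, expected enrolment in the second group falls from 3 × 0.657 = 1.97 to 3 × 0.441 = 1.32.
3. Mirror both changes in SAP 6.1. If the gate has already been passed, record in the study report how any delayed or replaced gate subjects were counted.

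The cost is wording in four protocol places and one SAP section. It needs no extra patients or analyses, and the DEC keeps its discretion.

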7.2.2 Safety Analysis Set (SAF)

All subjects who received at least one dose of trial drug (CyPep-1 or pembrolizumab in the combination arm). All analyses (except for PK) will be based on this analysis set.

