7.3 Dose Escalation Committee

The decisions on dose escalation and CyPep-1 MTD/RP2D will be taken by the Dose Escalation Committee after reviewing safety data (including DLTs) from all subjects who have entered Phase I of the trial and have completed the DLT observation period.

The DEC will review all data after all subjects in the highest dose cohort completed DLT observation period and before enrolment of subjects in the expansion cohort at RP2D in monotherapy and combination with pembrolizumab cohort can be initiated.

For Phase IIa of the trial, the decision to de-escalate the dose of CyPep-1 based on observed severity and relatedness of safety events (DLT/TLT criteria for CyPep-1) and to what dose (either dose level of the next lowest dose level from Phase I or 50-70% of current dose level), will also be made by the DEC after reviewing available safety data (including TLTs). Dose modifications for pembrolizumab in the combination arm will also be taken into consideration.

Based on the review of this data, recommendations will be made regarding the further conduct and the scientific and ethical integrity of the trial.

At the end of the DEC teleconference, the DEC will provide one of the following recommendations to the sponsor:

1. The trial is proceeding in line with the trial protocol.
2. The trial is not proceeding in line with the trial protocol and/or there is a possible change in the benefit/risk ratio.

The sponsor will act upon these recommendations as appropriate, i.e., the final decision will rest with the sponsor. The sponsor designee will notify the trial team (i.e., the responsible project manager at [REDACTED]) of the final decision regarding the DEC recommendations, including any actions to be taken. The [REDACTED] project manager will communicate the DEC recommendations and/or final decision of the sponsor to all investigators, Independent Ethics Committees (IECs) and Competent Authorities (CAs), if applicable.

DEC analyses are described in the *Cohort Management Plan* and are not in scope for this SAP.

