8.15 Calculation of Percentages

All percentages will be calculated against the total number of subjects in the population with non-missing observations at the specific timepoint, unless otherwise noted in table footnotes.

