9.6.1 CyPep-1

Exposure to and compliance with CyPep-1 will be summarized by cohort for the SAF by the following variables:

1. Number (%) of subjects exposed to CyPep-1 (overall and by cycle),
2. Number of CyPep-1 administrations (continuous variable),
3. Number (%) of subjects with one or more full dose of CyPep-1 not administered (overall and by cycle),
4. Number (%) of missed CyPep-1 administrations (overall; 0, 1, 2, 3, >3),
5. Number (%) of subjects with weekly CyPep-1 administration schedule during Cycle 1,
6. Average CyPep-1 dose per administration (continuous variable, see definition below),
7. Cumulative CyPep-1 dose (continuous variable, see definition below),
8. Average injected volume per administration (continuous variable, see definition below),
9. Cumulative injected volume (continuous variable, see definition below),
10. Number of injected lesions (overall; 1, 2, 3, 4, 5, >5),
11. Duration of treatment (continuous variable, defined in Section [8.4](#)),
12. Number (%) of times CyPep-1 not administered according to study protocol (overall; 0,1,2,3,>3).

A subject is counted as having been exposed to CyPep-1 in a cycle if the subject received CyPep-1 in given cycle.

Subjects with weekly CyPep-1 administration schedule during Cycle 1 are defined as subjects that received the first two doses of CyPep-1 within a 1-week interval.

For each subject, injected volume of CyPep-1 will be calculated for each administration of CyPep-1 as sum of injected volumes over all injected lesions. The CyPep-1 dose (mg) will be calculated as CyPep-1 concentration (mg/mL) multiplied with the injected volume of CyPep-1 (mL) for each administration of CyPep-1. An average injected volume will be calculated for each subject as mean of injected volume results of all CyPep-1 administrations and average dose will be calculated as mean of CyPep-1 dose results of all CyPep-1 administrations.

The cumulative dose (mg) will be calculated as sum of all doses received throughout the study. Cumulative injected volume (mL) will be calculated as sum of all injected volumes throughout the study.

CyPep-1 exposure and compliance data will be listed for all SAF subjects.

Statistical Analysis Plan

SMS-0571/CyPep-1

V3.0 Final

04-Jun-2024

Lesions targeted for injection (for all arms/cohorts) and lesion map information (for arm D only) will be listed for SAF.

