3. Finally, the itRECIST injected target lesion best response (grouped as itSD and better vs worse than itSD) will be presented by low/high volume groups for the SAF. Fisher's exact test will be used to compare distribution of response between the low and high-volume groups; p-value corresponding to the test will be presented.

The same analysis will be run excluding subjects with adrenocortical carcinoma (ACC) diagnosis. Subjects with ACC diagnosis will be identified based on coded value (i.e., MedDRA PT) of "Adrenocortical carcinoma" corresponding to *Histological type* reported on the *Primary Diagnosis* section of the *Primary Cancer eCRF* page.

Statistical Analysis Plan

SMS-0571/CyPep-1

V3.0 Final

04-Jun-2024

11 Safety Analysis

Safety will be assessed by means of physical examinations, body weight, vital signs, ECOG performance status, laboratory evaluations (hematology, biochemistry, coagulation, urinalysis), electrocardiograms (ECG), and recording of concurrent illness/therapy and adverse events. All assessments will be performed as indicated in the protocol Schedule of Assessments. Additional assessments may be performed as clinically indicated.

All safety analyses will be performed on the SAF.

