11.1.3 Analysis

All AEs will be presented by cohort/arm and overall.

An overview table of treatment-emergent AEs (TEAEs) will be produced, including counts and percentages of subjects (n) and events (#AE) for:

1. TEAEs,
2. TEAEs related to any study treatment (CyPep-1 or pembrolizumab),
3. TEAEs related to CyPep-1,
4. Serious TEAEs (TESAEs),
5. TESAEs related to any study treatment (CyPep-1 or pembrolizumab),
6. TESAEs related to CyPep-1,
7. CTCAE grade 3 or higher TEAEs,
8. CTCAE grade 3 or higher TEAEs related to any study treatment (CyPep-1 or pembrolizumab),
9. CTCAE grade 3 or higher TEAEs related to CyPep-1,
10. TEAEs leading to any study treatment (CyPep-1 or pembrolizumab) discontinuation,
11. TEAEs leading to CyPep-1 discontinuation,
12. TEAEs leading to pembrolizumab discontinuation,
13. TEAEs related to any study treatment (CyPep-1 or pembrolizumab) leading to any study treatment discontinuation,
14. TEAEs related to CyPep-1 leading to CyPep-1 discontinuation,
15. TEAEs related to any study treatment (CyPep-1 or pembrolizumab) leading to pembrolizumab discontinuation,
16. TEAEs leading to CyPep-1 dose reduction,
17. TEAEs leading to pembrolizumab dose reduction,
18. TEAEs leading to CyPep-1 dose interruption,
19. TEAEs leading to pembrolizumab dose interruption,
20. TEAEs leading to study discontinuation,
21. TEAEs leading to study discontinuation related to any study treatment (CyPep-1 or pembrolizumab),
22. TEAEs leading to study discontinuation related to CyPep-1,
23. Dose limiting toxicities (for Phase I and Phase IIa Arms A and C),
24. Treatment limiting toxicities (only for Arm B),
25. Fatal TEAEs,
26. Fatal TEAEs related to any study treatment (CyPep-1 or pembrolizumab),
27. Fatal TEAEs related to CyPep-1.

Adverse events will be coded based on the MedDRA (version specified in the *Data Management Plan*) for reporting by SOC and PT. SOC will be ordered in accordance with the international agreed upon sort order for SOC followed by descending order of overall PT incidence within the SOC.

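### The SAP reports DLT/TLT incidence only on the one-dose safety set, and the Arm C text neither excludes replacement after CyPep-1-related toxicity nor says whether an under-dosed subject counts in the 3+3

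*Protocol*

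**What the plan says.** Protocol 2.2.1 lists DLTs and TLTs as a primary endpoint. Protocol 3.1 and 3.1.2 tie them to Cycle 1: six weeks, with CyPep-1 planned in Weeks 1, 3 and 5.

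**Analysis sets.** Protocol 8.1.1 and SAP 7.2 define only a screened set, the SAF (at least one dose) and a PK set. Of the SAF, SAP 7.2.2 says: "All analyses (except for PK) will be based on this analysis set". SAP Section 11 repeats it: "All safety analyses will be performed on the SAF". In the adverse-event overview of SAP 11.1.3, two rows carry the endpoint: "Dose limiting toxicities (for Phase I and Phase IIa Arms A and C") and "Treatment limiting toxicities (only for Arm B"). SAP 8.15 takes percentages over subjects "with non-missing observations at the specific timepoint, unless otherwise noted in table footnotes". SAP 9.6.1 separately tabulates "Number (%) of subjects with one or more full dose of CyPep-1 not administered (overall and by cycle").

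**Replacement (Protocol 4.3.2).** For Arm C: "For Arm C, replacement for subjects who drop out for any reason, except DLTs, before the DLT observation period is completed is allowed" when fewer than three injections were received. The synopsis and SAP 6.1 repeat this. The Phase I sentence is also limited to dropouts, but it excludes subjects whose missing doses are due to CyPep-1-related toxicity. Arm B excludes toxicity related to either drug, and it also replaces any subject whose dose is delayed by more than 7 days in the TLT window.

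**Delays.** In Phase I and Arms A and C, a dose delayed by more than 7 days is omitted. The subject leaves the trial only after a delay of more than 6 weeks (synopsis, dose escalation and schedule; Protocol 4.3.1).

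**Committee review.** In Arm C, review of the lower dose follows once the third subject has finished the six-week window (Protocol 3.1). SAP 7.3 says that the Dose Escalation Committee (DEC) analyses are described in the Cohort Management Plan "and are not in scope for this SAP".

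**The concern.** A DLT rate is usually read as a rate among subjects with enough exposure and observation to show a DLT. Here the only planned denominator is everyone dosed once, so a subject who left after one injection, and the replacement for that subject, both count as DLT-free. That pulls the reported primary safety rate down.

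In Arm C the same gap bears on a decision. The step from 2 to 5 mg/mL injected into liver can rest on three subjects. The trigger for review is time on study, with no minimum number of injections. The replacement sentence would also allow a subject who dropped out with related toxicity short of a DLT to be exchanged for a new subject, whereas the Phase I and Arm B sentences would not.

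**Working it through.** The documents state no DLT rate or DLT-evaluable number, so there is no planned figure to reproduce.

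**1. Can an under-dosed Arm C subject reach review without dropping out?** The second injection is due on Day 15. Discontinuation needs a delay of more than 42 days, so it cannot occur before Day 15 + 42 = Day 57. The window is six weeks, or 42 days. A subject could therefore miss Days 15 and 29 and still finish the window after one injection. Under 4.3.2 that subject is not a dropout, so replacement is not provided for. Phase I has the same feature but is complete.

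**2. Effect on reporting.** This assumes one DLT/TLT and one non-evaluable subject. Planned numbers are from Protocol 8.2.

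| Arm | Evaluable | SAF |
|---|---|---|
| C, cohort 5 (9 planned − 3 in cohort 4 = 6; one replaced) | 1/6 = 16.7% | 1/7 = 14.3% |
| B (15 planned; one replaced) | 1/15 = 6.7% | 1/16 = 6.3% |
| A (9 planned; no replacement) | 1/8 = 12.5% | 1/9 = 11.1% |

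The 95% Clopper-Pearson interval is 0.4–64.1% for 1/6 and 0.4–57.9% for 1/7. Phase I had no DLTs (Protocol 1.6.1), so its rate is zero on either denominator.

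**3. Effect on escalation (illustration).** Assume equal, independent risk per injection; this is not in the documents. For a true three-injection DLT risk R, the per-injection risk is r = 1 − (1 − R)^(1/3), and the risk with k injections is 1 − (1 − r)^k. By the Protocol 3.1 table, P(escalate) = P(0 of 3) + P(1 of 3) × (1 − R)^3. Let one of the first three subjects receive k injections and all others three.

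Worked case, R = 0.30, k = 1: r = 0.1121. P(0 of 3) = 0.7² × 0.8879 = 0.435. P(1 of 3) = 0.1121 × 0.49 + 2 × 0.3 × 0.7 × 0.8879 = 0.428. P(escalate) = 0.435 + 0.428 × 0.343 = 0.582.

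| R | k = 3 | k = 2 | k = 1 |
|---|---|---|---|
| 0.10 | 0.906 | 0.917 | 0.929 |
| 0.20 | 0.709 | 0.738 | 0.770 |
| 0.30 | 0.494 | 0.535 | 0.582 |
| 0.40 | 0.309 | 0.352 | 0.403 |

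The documents do not say how often doses are missed. Let each subject have a chance m of being under-dosed for reasons other than toxicity. Then p = (1 − m)R + m × risk(k), and P(escalate) = (1 − p)^3 + 3p(1 − p)^5. The rise in percentage points at an assumed m of 5 / 10 / 20% is:

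| R | One injection missed | Two missed |
|---|---|---|
| 0.10 | 0.3 / 0.5 / 1.0 | 0.5 / 1.1 / 2.1 |
| 0.30 | 0.9 / 1.8 / 3.7 | 1.9 / 3.9 / 7.9 |
| 0.40 | 0.9 / 1.8 / 3.7 | 2.0 / 4.1 / 8.5 |

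**4. How wide is the toxicity route?** One path is a related ALAT/ASAT rise above 7.5 × ULN lasting 8 to 14 days without the bilirubin rise, which the transaminase exception in Protocol 3.1.2 exempts. If it is Grade 3, treatment is interrupted (Protocol 5.3.6.1), and a dose delayed by more than 7 days is omitted. Replacement then still requires that the subject drop out.

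**The case against.** Several points narrow this, and most of them stand.

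- Protocol 4.3.1 describes dropouts as subjects who withdraw consent, cannot or will not comply, or are lost to follow-up. It says that stopping CyPep-1 for safety is not necessarily withdrawal. On that reading, related toxicity alone does not trigger replacement in Arm C. The sentence's own exception for DLTs suggests looser usage, so this leaves an ambiguity.
- The DLT definition has a catch-all for toxicity judged a clinically significant hazard, which could capture the liver event in step 4. Arm C is also said to follow the Phase I procedures in Section 3.1, where the toxicity exclusion appears. Against that, the Arm C sentence itself omits it in three places.
- The Cohort Management Plan may already say who counts. The DEC includes the investigators and the medical monitor, who can see missed doses.
- Analysing all treated subjects is a stated choice. Missed doses are tabulated by cycle, and DLTs and TLTs are listed, so a reader could recompute the rate in arms this small. SAP 8.15 also lets a table footnote set another denominator, although neither document states one for this endpoint.

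What remains is that no rate among evaluable subjects is planned, the Arm C exclusion is missing, and neither document has a counting rule for an omitted dose.

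**Conclusion.** The point holds as a minor one. The SAF-only denominator dilutes the DLT/TLT rate by 0.4 to 2.4 percentage points in the examples above, and only if a DLT/TLT and a non-evaluable subject both occur. These shifts are small beside the interval around 1/6. The Arm C replacement sentence is out of line with Phase I and Arm B, although the route by which this matters is narrow.

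A reader might infer that Arm C escalated, or would escalate, on inadequately exposed subjects, or that toxic cases can be quietly exchanged. The documents do not support either. They do not show that any subject was under-dosed, they place DEC analyses in a plan that was not available, and the dropout wording and hazard item limit the exchange. A reader might also take the dropout-only limit as peculiar to Arm C, but Phase I has it too. The escalation figures apply only if the Cohort Management Plan has no counting rule, and they depend on the assumed per-injection risk, missed-dose rate and true DLT rate.

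**What to change.** 1. In SAP 7.2, add a DLT/TLT-evaluable set: subjects who received all three scheduled Cycle 1 CyPep-1 injections (Days 1, 15 and 29) and completed the six-week window, or who had a DLT/TLT. In SAP 11.1.3, report DLT/TLT incidence on this set beside the SAF.
2. Add the Phase I exclusion for CyPep-1-related toxicity to the Arm C replacement sentence in the synopsis, Protocol 4.3.2 and SAP 6.1. On its own, together with item 3, this could leave a cohort of two countable subjects that the 3+3 table cannot resolve. So count an Arm C subject who misses Cycle 1 injections because of related toxicity as having a DLT for the 3+3, and include that subject in the evaluable set. This matches TLT item 8 for Arm B (more than 25% of doses missed for drug-related events), since one of three is 33%.
3. If Arm C is still enrolling and the Cohort Management Plan has no such rule, count only evaluable subjects toward the three and the six, and allow replacement of those not evaluable for reasons other than toxicity. Otherwise cite the plan's rule in SAP 7.3.

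The cost is one extra table column, an occasional replacement subject, a slightly more conservative 3+3, and a short protocol amendment only if Arm C is still enrolling. Item 1 is useful even if enrolment has closed.
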